We propose a longitudinal, interventional, case-crossover study design to examine whether expanded tampon shape affects VMB composition during, and in between menses. We will recruit 20 women from the University of Michigan, Ann Arbor to use Tampax® Pearl® Regular Tampons (expand into a rectangular prism-like shape) and Playtex® Gentle Glide® 360°® Regular Tampons (expand into a conical shape) for one menstrual cycle each, in a randomly assigned order. We will obtain twice-weekly self-collected vaginal swabs for a 2-3 week baseline window before the first menstrual cycle with an assigned tampon, followed by the two menstrual cycles with assigned tampon use, and finishing with one menstrual cycle with menstrual product use according to each subject's normal habits. DNA will be isolated from the vaginal swabs, and the bacterial 16S rRNA encoding genes will be amplified by PCR. Sequencing will be performed using the MiSeq Illumina platform, and analyzed to answer the above questions.

Outcomes and aims

- Primary Outcome: Change in relative abundance of *Lactobacillus* species from: baseline to the end of first menstrual cycle, baseline to the end of second menstrual cycle, and baseline to the end of third menstrual cycle (approximately 14 weeks)
- Secondary Outcome: Change in relative abundance of *Gardnerella vaginalis* from: baseline to the end of first menstrual cycle, baseline to the end of second menstrual cycle, and baseline to the end of third menstrual cycle (approximately 14 weeks)
- Exploratory Outcomes
 - To characterize intra-woman, during-menses changes in VMB composition caused by (see Methods – Study Design and Methods – Whole Community Analysis & Statistics sections for notes on causal inference) changing the expanded tampon shape of tampon used.
 - Hypothesis 1: VMB composition will vary between menses with Tampax® Pearl® Regular Tampon use and Playtex® Gentle Glide® 360°® Regular

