Tampon use because the different expanded shapes of the two tampons will alter the vaginal environment differently and thus promote growth of different taxonomic groups. The primary structural difference between Tampax® Pearl® Regular Tampons and Playtex® Gentle Glide® 360°® Regular Tampons is that, once inserted into the vagina, Tampax® Pearl® Regular Tampons expand axially into a rectangular prism-like shape, while Playtex® Gentle Glide® 360°® Regular Tampons expand radially into a conical shape. The radial expansion of the Playtex® Gentle Glide® 360°® Regular Tampons likely results in increased surface area of the tampon that is in contact with the vaginal epithelium as compared to the Tampax® Pearl® Regular Tampons. This may allow for increased absorption of menses by the Playtex® Gentle Glide® 360°® Regular Tampons as compared to the Tampax® Pearl® Regular Tampons, resulting in differing growth conditions in the vagina during Playtex® Gentle Glide® 360°® Regular Tampon use and Tampax® Pearl® Regular Tampon use.

- To characterize intra-woman, between-menses changes in VMB composition caused by (see Methods – Study Design and Methods – Whole Community Analysis & Statistics sections for notes on causal inference) changing the expanded shape of tampon used.
 - Hypothesis 2.1: Persistence of VMB changes observed during menses caused by changing the expanded shape of the tampon used will vary dependent on baseline VMB community type such that VMB changes will persist for greater time between menses in women with typically diverse VMB that confer reduced colonization resistance compared to a *Lactobacilli* dominated VMB [Borovkova 2011, Lopes 2011, Borges 2014, reviewed in Hickey 2012].
 - Hypothesis 2.2: Within women with *Lactobacilli* dominated baseline VMB, persistence of VMB changes observed during menses caused by changing expanded tampon shape will vary based on the degree of reduction of *Lactobacilli* abundance during menses such that changes resulting in greater reductions of *Lactobacilli* abundance will persist for greater time between menses.

Methods

Recruitment

- We will recruit 40 women from the University of Michigan, Ann Arbor during the Winter 2017 semester.
 - We will make an in-person announcement in Women’s Studies 400: Women’s Reproductive Health (taught by [name], Dept. of OB/GYN) according to the following script:

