 - Hello everyone, we are here to recruit forty healthy female students to participate in our study examining the impact of changing tampon use on the composition of the vaginal microbiota. The study period will consist of a baseline window after a subject’s last period and three full menstrual cycles. For the first two menstrual cycles, each subject will use Tampax® Pearl® Regular

Tampons and Playtex® Gentle Glide® 360°® Regular Tampons for one menstrual cycle each, in a randomly assigned order. For the third menstrual cycle, each subject will use menstrual products according to their normal habits. For the course of the study, approximately 4 months, subjects will self-collect vaginal swabs twice a week. These samples will be used for bacterial community analysis to assess the composition of the vaginal microbiota at each time point, and compare composition during periods using different tampons and determine how long these changes persist between periods. For the first two menstrual cycles, the study tampons and Always® Infinity® Regular Pads will be provided to subjects free of charge. Additionally, each subject will receive \$20. In order to be eligible to participate in this study, you must be at least 18 years old, have regular menstrual cycles that last 3-5 weeks with periods that last for at least 4 days, currently use tampons, and be in good general and vaginal health. You are ineligible to participate if you are pregnant or planning on becoming pregnant in the next 4 months, if you have difficulty using tampons, if you currently have or have had toxic shock syndrome (TSS), if you currently have a sexually transmitted infection (STI) or urinary tract infection (UTI), if are currently using antibiotics or antifungals or have used antibiotics or antifungals within the last month, or if you have an autoimmune condition. If you are interested in participating in this study, please email ([contact]) and then we will set up an enrollment meeting.

- We will also pass out flyers describing the objective of the study, the duration of subject participation, subject responsibilities, subject compensation, eligibility requirements, and exclusion criteria. It will also include the email address for setting up enrollment meetings. We will also post these flyers at the Michigan Union and other places around central campus.
- We will also post the study in UMHealthResearch.org.

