- Exclusion criteria: Respondents will be excluded if they are pregnant or are planning on becoming pregnant during the study; have difficulty using tampons; currently have, or have had TSS; currently have an STI; currently have a UTI; are currently using current antibiotics, or used antibiotics within 4 weeks prior to enrollment; are currently using current antifungals, or used antifungals within 4 weeks prior to enrollment; or have an autoimmune condition.

Study Design

- This study will be a longitudinal, interventional, case-crossover study with three exposure levels:
 - Experimental exposure levels: Each subject will use Tampax® Pearl® Regular Tampons and Playtex® Gentle Glide® 360°® Regular Tampons for one menstrual cycle each, in a randomly assigned order.
 - Control exposure level: Each subject will use menstrual products according to their normal habits for a third menstrual cycle.
 - A case-crossover design ensures exchangeability between treatment windows within each subject for all time invariant characteristics. Under exchangeability and the assumptions of an intent-to-treat analysis (covered in Methods – Whole Community Analysis &

Statistics), the actual outcome observed under one treatment for an individual equals the counterfactual outcome under that treatment for that individual, so association between expanded tampon shape and VMB composition represents a causal relationship. This study design and the intent-to-treat analytic strategy will allow us to make causal inference in reference to the effect of expanded tampon shape on VMB composition.

- Vaginal swabs will be self-collected by each subject twice weekly for four different exposure windows (Fig. 1):
 - A 2-3 week baseline window after the last menstrual period prior to enrollment; 4-6 baseline samples per subject.
 - One menstrual cycle using the Tampax® Pearl® Regular Tampons; 8 samples.
 - One menstrual cycle using Playtex® Gentle Glide® 360°® Regular Tampons; 8 samples.
 - The final menstrual cycle with menstrual product use according to the subject's normal habits; 8 samples for the subject's normal habits.

[figure not shown]

Figure 1: Study design.

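### The Lactobacillus and Gardnerella outcomes are indexed by cycle number, and no named test or contrast compares either of them by assigned tampon

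*Combined protocol and SAP*

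**What the plan says.** All references are to the combined protocol and SAP.

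- **Outcomes and aims.** The primary outcome is the change in relative abundance of *Lactobacillus* "species from: baseline to the end of first menstrual cycle, baseline to the end of second menstrual cycle", followed by baseline to the end of the third cycle. The secondary outcome has the same three time points for *Gardnerella vaginalis*. Neither names a tampon. The comparison of shapes appears under the exploratory outcomes, on overall community composition.
- **Study Design.** The two tampons are used "for one menstrual cycle each, in a randomly assigned order". The control level always comes last: "Each subject will use menstrual products according to their normal habits for a third menstrual cycle". Swab windows are listed by product, with 8 swabs per cycle and "4-6 baseline samples per subject".
- **Recruitment script.** The samples will be used to "compare composition during periods using different tampons and determine how long these changes persist between periods".
- **Whole Community Analysis & Statistics.** Relative abundances are to be calculated. The one named hypothesis test, Mann-Whitney or Kruskal-Wallis, is applied to within-subject theta-YC distances by tampon shape. The intent-to-treat paragraph, like Study Design, claims causal inference about shape.
- **Persistence.** Hypothesis 2.1 expects that "VMB changes will persist for greater time between menses in women with typically diverse VMB". Hypothesis 2.2 expects that "persistence of VMB changes observed during menses caused by changing expanded tampon shape will vary based on the degree of reduction of" *Lactobacilli* abundance. Background describes the baseline window as "followed by the two menstrual cycles with assigned tampon use", and no washout is described.

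**The concern.** The stated question is whether expanded tampon shape affects the vaginal microbiota. Because order is randomised, cycle number does not identify the product, and the third cycle adds nothing to a Tampax-Playtex comparison. An analyst who reports the primary and secondary outcomes exactly as listed will describe how the two taxa move over about 14 weeks. That is relevant to the broader aim under Benefits, but it is not an estimate of the shape effect.

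The causal claim about shape would then rest on an exploratory whole-community distance. Any statement about *Lactobacillus* or *Gardnerella* by product would need a contrast, and a choice of swabs, that could be settled after the results are known. Neither the end-of-cycle value nor the baseline value is tied to particular swabs.

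**Working it through.** The plan gives no power, alpha, SD, effect size or carryover fraction, so there is no figure of its own to reproduce. Steps 1 to 3 rest on the text and algebra. Step 4 is illustration only.

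**1. What each by-cycle change contains**

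| Order group | Cycle 1 | Cycle 2 | Cycle 3 |
|---|---|---|---|
| Tampax first | Tampax | Playtex | usual products |
| Playtex first | Playtex | Tampax | usual products |

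Let τ be the Tampax minus Playtex effect, π the period effect (cycle 2 minus cycle 1), and k the number of the 20 women who use Tampax first. With no carryover,

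mean(cycle 2) − mean(cycle 1) = π − (2k/20 − 1)τ.

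- k = 10: the multiplier is 0, so no τ remains.
- k = 6: 12/20 − 1 = −0.4, so the difference is π + 0.4τ.
- k = 14: 28/20 − 1 = +0.4, so the difference is π − 0.4τ.

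The plan does not state the order ratio. Under simple randomisation k lies between 6 and 14 with probability 0.959.

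**2. What is recoverable**

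Let d be each woman's cycle 2 minus cycle 1 value. The expected d is π − τ if Tampax came first and π + τ if Playtex came first. Half the difference between order groups is τ, free of π. The woman's baseline is subtracted in both cycles and cancels from d. The data therefore support the contrast; the plan does not state it.

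**3. Whether the theta-YC test can stand in**

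Distance = 1 − Σab / (Σa² + Σb² − Σab). Take three OTUs: *Lactobacillus* A, *Lactobacillus* B, other.

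- *Lactobacillus* falls from 80% to 60%, (0.8, 0, 0.2) to (0.6, 0, 0.4): 1 − 0.56/(0.68 + 0.52 − 0.56) = 0.125.
- The reverse, a rise from 60% to 80%: also 0.125.
- 20 points of A replaced by B, total *Lactobacillus* still 80%, (0.8, 0, 0.2) to (0.6, 0.2, 0.2): 1 − 0.52/(0.68 + 0.44 − 0.52) = 0.133.

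A fall and a rise give the same distance, and no change in total *Lactobacillus* gives a slightly larger one. The third case is possible because the plan reports that 6 *Lactobacillus* types could be distinguished.

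**4. Illustrative precision of the missing contrast**

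Assumptions: 20 complete women, 10:10 order, normal d with SD 1, two-sided 5%. If a fraction f of the cycle 1 product difference persists into cycle 2, the contrast estimates τ(1 − f/2). Noncentrality = 2τ(1 − f/2)/√(1/10 + 1/10), with 18 df. For τ = 0.5 and f = 0 this is 1/0.447 = 2.24, giving 56.2%.

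| f | τ = 0.5 SD | τ = 1 SD |
|---|---|---|
| 0 | 56.2% | 98.8% |
| 0.25 | 45.7% | 95.9% |
| 0.5 | 35.5% | 88.7% |
| 1 | 18.5% | 56.2% |

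- Mann-Whitney version, 20,000 simulations: 50.9% and 97.9% at f = 0; 31.4% and 85.3% at f = 0.5.
- 8:8 completers, f = 0: 46.1% and 96.0%.
- Cycle 1 compared between order groups, which no earlier study tampon can affect: SD = 1/√(2(1 − ρ)), where ρ is the correlation between a woman's two cycles. At ρ = 0.5 power is 18.5% and 56.2%. Over ρ = 0.3 to 0.7 it runs from 24.0% to 13.0% at 0.5 SD and from 70.6% to 37.5% at 1 SD.
- Fading by the end of the cycle: if half or a quarter of a 1 SD menses effect remains, τ is 0.5 or 0.25, and power at f = 0 is 56.2% or 18.5%.

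**The case against.** The strongest reply is that an outcome list gives variables and time points and need not state the comparison. The rest of the plan is organised by product: exposure levels and swab windows under Study Design, the recruitment script, and the intent-to-treat paragraph. The two taxa are part of the composition that paragraph refers to, so grouping by assigned product is the natural reading. Much of this stands. It shows intent, and it means the gap is in specification. It does not supply a test, a contrast or a swab set for either outcome.

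Other parts of the reply also stand:

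- The plan nowhere says it will compare the plain cycle 1 and cycle 2 means, so step 1 shows what the indexing carries. It does not criticise a declared test.
- Relative abundances are to be calculated, so direction would be visible descriptively.
- If a cycle is counted from the start of menses, its end may fall weeks after the assigned tampon was used, whereas Hypothesis 1 expects the shape effect during menses. A product contrast at the end of the cycle alone could miss it.
- The documents support no value of f. The hypotheses speak of persistence between menses and do not say that it reaches the next cycle's outcome.

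A reader might infer that the trial cannot answer the shape question. The documents do not support that: assigned order is known for every woman, and step 2 recovers τ. A reader might also infer that carryover will bias the result or that 20 women are too few. Both would need inputs that the plan does not give.

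**Conclusion.** The point holds as a gap in specification that should be fixed; it is not a fatal flaw in the design. No section names a test or contrast of *Lactobacillus* or *G. vaginalis* relative abundance by assigned tampon. As listed, the two outcomes give a time course in which cycles 1 and 2 each mix both products, and the causal claim about shape rests on an exploratory distance that has no sign.

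This conclusion rests on the text and the crossover algebra. The multiplier of zero on the product effect assumes a 10:10 order and no carryover. The power figures are illustrations and say nothing about what this trial will find. Carryover matters only in that the plan hypothesises persistence and describes no washout, so a product contrast needs its assumption stated.

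**What to change.** 1. Keep the three by-cycle changes as descriptive results.
2. For each outcome, add one pre-specified within-woman Tampax-versus-Playtex contrast in relative abundance, adjusted for period. Name one analysis: a model with product and period fixed and woman random, or a Mann-Whitney test of cycle 2 minus cycle 1 differences between the two order groups.
3. State which swabs form the baseline value (for example the mean of the 4-6 baseline swabs) and which of the 8 swabs form the end-of-cycle value.
4. Report the same product contrast on menses swabs alongside it, because the shape effect is hypothesised during menses.
5. State the no-carryover assumption. Show the cycle 1 comparison between order groups, with its confidence interval, as a sensitivity estimate and not as a test.
6. Set all this before the sequence data are examined by assigned product. The document is dated March 2018 and recruitment is given as Winter 2017, so it cannot be assumed that sequencing is still pending. If the data have already been examined, label the contrast with the date on which it was fixed.

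The cost is amended text and a little more analysis, with no new swabs or visits. The downside is that the cycle 1 sensitivity estimate is a comparison between women and will be imprecise.

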A considerable volume of work has also been conducted to characterize the fluctuations of the VMB across the menstrual cycle. While some studies (both culture-dependent and culture-independent) have reported no change in community composition across the menstrual cycle [Sautter 1980, Wilks 1987, Gajer 2012, Hickey 2013], others have reported varying relative abundances of aerobic and anaerobic bacteria across the cycle [Bartlett 1977] or a greater proportion of non-*Lactobacillus* species during menses [Priestley 1997, Eschenbach 2000, Srinivasan 2010, Lopes 2011, Gajer 2012, Hickey 2013]. In light of these findings, in particular those of Gajer et al. (2012) and Hickey et al. (2013), it is currently thought that the degree and type of VMB fluctuation seen across the menstrual cycle varies between women [Lopes 2011, Chaban 2014]. Further, the increased abundance of non-*Lactobacilli* species seen during menses is of particular interest given the changes to vaginal innate immune cell presence [Hill 1992], temperature [Hill 2010], oxygen and carbon dioxide concentrations [Hill 2005], and volatile fatty acid concentrations [Preti 1975] that occur during menses. These changes alter the growth conditions present in the vagina, and as such, may promote the growth of certain bacterial species over others. Given that non-*Lactobacilli* species are often present in greater abundance during menses, it is possible that the conditions of the vagina during menses could promote their growth and potentially shift a *Lactobacilli*-dominated VMB to a diverse VMB and promote BV. Moreover, the changes to vaginal temperature, dissolved gas concentrations, and volatile fatty acid concentrations that occur during menses have been shown to be exacerbated by tampon use [Preti 1975, Hill 2005, Hill 2010], suggesting that tampon use may compound any VMB changes that occur during menses.

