- We will respond to interest emails according to the following script in order to set up enrollment meetings with each interested student:
 - Dear [name],

Thank you for your interest in participating in this study. The next step is to set up an enrollment meeting at which you will be assigned a random study ID number, review the informed consent document for the study, give informed consent to participate in the study if you choose to, complete an online enrollment survey, and receive the tampons, pads, and vaginal swabs for the study. The following times are available for the enrollment meeting:

Monday 9:30 AM – 4:15 PM

Tuesday 1:30 PM – 4:00 PM
Wednesday 11:00 AM – 4:15 PM
Thursday 1:30 PM – 4:15 PM

Please respond to this email with your preferred day and time for the enrollment meeting. The meeting will take approximately 30 minutes.

Thanks

- At the enrollment meeting we will obtain informed consent from each student, assign a random ID number to the student, administer the baseline survey (assess eligibility, collects data on covariates (covered in Methods subsection Study Design)) on a lab computer using Qualtrics, review subject responsibilities with each student, and distribute study materials including 30 vaginal swabs, vaginal swab instructions, 30 collection day surveys, 24 Tampax® Pearl® Regular Tampons, 24 Playtex® Gentle Glide® 360°® Regular Tampons, 24 Always® Infinity® Regular Pads with wings to each subject. All research data will be kept in files that include the subject ID number, but not name or other information that is likely to allow someone other than the researchers to link the data to a subject. These files will be maintained in a password protected lab file manager. We will enroll the first 20 eligible students who schedule an enrollment meeting.
- Inclusion criteria: Subjects must be 18 years of age or older; have regular menstrual cycles lasting 21-35 days with menses for at least 4 days; be a current tampon user; be in self-reported good general health; and be in self-reported good vaginal health.

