- Intent to treat analysis: This analytic strategy assumes each subject's actual exposure is exactly as it was assigned (complete compliance with assigned interventions, exposure fixed for each subject during each treatment window, complete follow-up). The implications of this analytic approach in conjunction with the within-subject exchangeability produced by the case-crossover design (covered in Method – Study Design section) is that the actual outcome observed under one treatment for a subject equals the counterfactual outcome under that treatment for that subject, so association between expanded tampon shape and VMB composition represents a causal relationship. This study design and analytic strategy will allow us to make causal inference in reference to the effect of expanded tampon shape on VMB composition.

Benefits

- This study will help to provide information on whether the use of tampons is associated with changes in the VMB over the course of a menstrual cycle. If there are associated changes in the VMB associated with tampon use then our research could help provide information on a potentially modifiable time point to help improve the vaginal health of women.

Risks

- No more than minimal risk
 - Discomfort with tampon use - rare - we are recruiting women that are currently tampon users.
 - Toxic shock syndrome (TSS) - rare- the rates of TSS with currently available tampons are extremely low. Each women will be given manufacturers instructions which include ways to decrease the risk of TSS.

- Discomfort with vaginal swab collection - rare- the Starplex swabs have been used in numerous trials by our lab without any problems given that the swab is considerably smaller than the size of the tampon introducer. Additionally, detailed instructions on sample collection are provided.
- Disclosure of subject information - rare- each subject will be provided a unique ID for the data collected (samples and surveys). All collected information will be maintained in a password protected lab file manager.
- All recruited women in this trial will be active tampon users and thus we do not foresee any likelihood of these risks interfering with the subjects day to day living.

Incentives

- Each subject will receive a \$20 gift card for participating in this study.

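### The primary and secondary outcomes are changes from a menses-free baseline, indexed by cycle number and with no swabs or phase named, so no reading of them isolates the Tampax-Playtex effect

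*Combined protocol and SAP*

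**What the plan says.** Outcomes and aims sets the primary outcome as change in relative abundance of Lactobacillus from "baseline to the end of first menstrual cycle, baseline to the end of second menstrual cycle", and to the end of the third cycle at about 14 weeks. The secondary outcome has the same form for Gardnerella vaginalis. The changes are labelled by cycle number, not by tampon.

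Study Design gives the windows. Baseline is "A 2-3 week baseline window after the last menstrual period prior to enrollment; 4-6 baseline samples per subject", and it closes before the first assigned cycle. Then comes "One menstrual cycle using the Tampax® Pearl® Regular Tampons; 8 samples", the same for Playtex in randomised order, and a third cycle on usual products, also with 8 swabs.

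The Background treats menstruation as a possible cause of change in its own right. It cites studies with a larger non-Lactobacillus share during menses, and says of those species that "it is possible that the conditions of the vagina during menses could promote their growth". It also cites studies that found no change over the cycle.

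The only test named, in Whole Community Analysis & Statistics, is of within-subject distances by tampon shape. The during-menses comparison of the two tampons is listed as exploratory. Benefits says the study will inform "whether the use of tampons is associated with changes in the VMB over the course of a menstrual cycle".

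**The concern.** The two ends of each change score can sit in different phases of the cycle. Baseline lies between periods, while each later window includes a period. A woman whose Lactobacillus share falls during every period, whatever product she uses, can show a decrease from baseline with no tampon effect at all. Whether she does depends on which swabs form the end-of-cycle value and how the 4-6 baseline swabs are combined, and the plan states neither.

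The indexing is a second problem. Tampon order is randomised, so cycle 1 contains Tampax users and Playtex users together, and so does cycle 2. The change at a numbered cycle is not an effect of either product. At stake is whether the headline result answers the study's own question about tampon shape, and whether a fall from baseline gets read as an effect of tampon use.

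**Working it through.** **Inputs from the documents.** Two swabs a week; baseline 2-3 weeks; 8 swabs per cycle; 30 swabs issued (Recruitment); 20 women enrolled; women must "have regular menstrual cycles lasting 21-35 days with menses for at least 4 days"; tampon supply planned for 6 days per cycle (Menstrual Products), used here as the upper working value for menses length. **Assumed, because the documents give none:** the drop D in Lactobacillus share caused by menses alone, the SD of within-woman change, and the test.

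**1. The schedule reproduces.** Baseline: 2 × 2 to 2 × 3 = 4-6 swabs. A 28-day cycle: 2 × 28/7 = 8. Total: 4-6 + 3 × 8 = 28-30, against 30 issued. Time: 2-3 weeks + 3 × 4 weeks = 14-15 weeks, against about 14. The last time point is therefore the end of a full third cycle.

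**2. Menses swabs per cycle.** k = 2m/7 for m days of menses. m = 4 gives 8/7 = 1.1; m = 6 gives 12/7 = 1.7. That is 14%-21% of 8 swabs.

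**3. Apparent change from baseline when the true tampon effect is zero.**

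| Swabs used for the cycle value | Formula | D = 0 | D = 10 | D = 30 |
|---|---|---|---|---|
| Menses swabs only | −D | 0 | −10 | −30 |
| Mean of all 8 | −D × k/8 | 0 | −1.4 to −2.1 | −4.3 to −6.4 |
| Last swab, menses effect not persisting | 0 | 0 | 0 | 0 |

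**4. What the last swab measures.** If a cycle starts with its menses, a 28-day cycle with 6 days of menses ends 28 − 6 = 22 days after bleeding stops, so the last swab comes about 3 weeks after the last tampon. It captures only what has persisted until then.

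**5. Pooling by cycle number.** Let a and b be the mean changes under Tampax and Playtex, p the share of women using Tampax first, and c1 and c2 effects of cycle number.

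- Cycle 1 estimates p·a + (1 − p)·b + c1.
- Cycle 2 estimates (1 − p)·a + p·b + c2.
- Their difference is (2p − 1)(a − b) + c1 − c2.

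With an even split (p = 0.5, assumed; no allocation ratio is given) the product effect drops out of the difference entirely, and each cycle on its own shows only the average of the two products. This holds whichever swabs are used.

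**6. The product contrast.** Within a woman, (Tampax − baseline) − (Playtex − baseline) = Tampax − Playtex. Baseline and any menses effect common to both cycles cancel for every D.

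**7. Illustrative error rate for the cycle-mean reading.** One-sample t-test of change against zero, n = 20, two-sided 0.05 (critical t 2.09), counting only significant decreases; noncentrality = (D × k/8)/(SD/√20).

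| D | SD | Noncentrality (k = 1.1, 1.7) | Chance of a false decrease |
|---|---|---|---|
| 0 | any | 0 | 2.5% |
| 10 | 15 | 0.43, 0.64 | 6%-9% |
| 10 | 30 | 0.21, 0.32 | 4%-5% |
| 30 | 15 | 1.28, 1.92 | 23%-44% |
| 30 | 30 | 0.64, 0.96 | 9%-15% |

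If menses swabs alone were set against baseline, D = 10 would give 81% at SD 15 and 29% at SD 30.

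**The case against.** The outcome is written as change to the end of each cycle. If cycles begin with menses, that end is intermenstrual, baseline is intermenstrual too, and both follow a period. Menses bias is then near zero unless a menses effect lasts for weeks. This stands, and it limits the point. A reader might infer that the primary outcome is necessarily confounded by menstruation. The documents do not support that: neither a cycle mean nor a menses-versus-baseline comparison is specified, and the design figure is not shown in the text available. A late swab also has a purpose, since persistence between menses is a stated exploratory aim. But it then measures persistence, not what happens while the tampon is in use.

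The numbers are open to attack as well. The drop, the SD and the one-sample t-test are all absent from the plan, and the Background cites studies with no menses effect. A reader might take 23%-44% as the plan's false-positive rate. It is not: it needs a cycle mean, a 30-point drop and an SD of 15, and doubling the SD brings it to 9%-15%.

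The causal claims are confined to tampon shape, where a common menses effect cancels, and the Benefits wording is cautious. Both are fair. A reader might also infer that omitting a tampon-free menses is a design error; for a question about shape it is a choice of scope. What remains is that the primary outcome is not written as the shape contrast, and that the Benefits sentence goes beyond that scope. Randomised order, the usual-product cycle and the menses flag could each help, but the plan ties none of them to the primary outcome.

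**Conclusion.** The point holds in a conditional form and should be corrected; it does not undermine the design. Three statements do not depend on assumed values:

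- The swabs and phase behind the baseline and end-of-cycle values are undefined.
- Change indexed by cycle number pools the two products and does not estimate the Tampax-Playtex effect.
- All participants are current tampon users and no tampon-free menses is assigned, so an effect of tampon use cannot be separated from menstruation.

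Mixing of menses with exposure is a consequence of some readings only. Its size is unknown: 0-6.4 points for a cycle mean with an assumed drop of 0-30 points, the whole drop if menses swabs are set against baseline, and about zero for a last intermenstrual swab. That last reading avoids the bias by measuring about 3 weeks after exposure.

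**What to change.** 1. Make the main comparison the within-woman Tampax minus Playtex difference in Lactobacillus relative abundance (and Gardnerella vaginalis for the secondary outcome) on swabs flagged as menses, allowing for period. State how a woman's menses swabs in one cycle are combined.
2. Restrict any change from baseline to intermenstrual swabs matched on cycle day, and report it by product. The baseline survey records the first day of the last period, each swab is dated, and each swab survey records menses status.
3. Limit the Benefits statement to a comparison of two tampon products.

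This is a change of wording and analysis and needs no new samples. The costs are modest. The baseline comparison loses about 1-2 of 8 swabs per cycle. The main comparison rests on those same 1-2 swabs per woman per cycle. Cycle-day matching is approximate: swabs are about 7/2 = 3.5 days apart, and in later cycles the start of menses may be known only to that precision unless the survey item on changes in menses captures the date. The contrast removes a menses effect common to both cycles, but not any carry-over from the first tampon into the second cycle.
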